9.2 Sample Size Determination

The planned enrollment for this study is **approximately** 45 **patients**. The sample size is based on feasibility rather than on statistical considerations. Given a true probability of a primary endpoint event of 38%, the expected 95% upper confidence limit with 45 subjects would be 53.5%. The 38% probability is based **on** the SAE rate in first 3 days of cycle 1 and first 2 days of cycle 2 from the previous MRD study (BLAST). Based on these assumptions, we expect to observe approximately 17 subjects who will experience the primary endpoint which should provide an initial indication of the timeliness of the therapeutic intervention when outpatient blinatumomab in administered in conjunction with remote digital monitoring.

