11.8 Appendix 8. Protocol-specific Definitions

Cytokine Release Syndrome (CRS)

A supraphysiologic response following the administration of blinatumomab therapy that results in the activation or engagement of endogenous or infused T cells and/or other immune effector cells. Symptoms can be progressive, must include fever (\square G1) at the onset, and may include hypotension, capillary leak (hypoxia) and end organ dysfunction.

Table 2 ASTCT CRS Consensus Grading

CRS Parameter	Grade 1	Grade 2	Grade 3	Grade 4
Fever*	Temperature ≥38°C	Temperature ≥38°C	Temperature ≥38°C	Temperature ≥38°C
	•			
Hypotension	None	Not requiring vasopressors	Requiring a vasopressor with or without vasopressin	Requiring multiple vasopressors (excluding vasopressin)
			And/or [†]	
Нурохіа	None	Requiring low-flow nasal cannula [†] or blow-by	Requiring high-flow nasal can- nula [†] , facemask, nonrebreather mask, or Venturi mask	Requiring positive pressure (eg, CPAP, BiPAP, intubation and mechanical ventilation)

Organ toxicities associated with CRS may be graded according to CTCAE v5.0 but they do not influence CRS grading.

Source: Lee et al, 2018.

Fever

Fever as defined in the Common Terminology Criteria for Adverse Events (CTCAE) v5.0 is "a disorder characterized by elevation of the body's temperature above the upper limit of normal (ULN)," and a temperature $\geq 38.0^{\circ}\text{C}$ (100.4°F) (for this study, axillary temperature $\geq 37.0^{\circ}\text{C}$ [99.4°F]) is considered grade 1 fever.

For this study, any temperature $\geq 38.0^{\circ}\text{C}$ (100.4°F) maintained for a minimum of 10 minutes will generate an alert. As this study will rely on the fever scout the equivalent alert values from the fever scout will be set at $\geq 37.0^{\circ}\text{C}$ (99.4°F).

CTCAE v5.0 Fever

1 38.0 - 39.0°C (100.4 - 102.2°F)

2 > 39.0 - 40.0°C (102.3 - 104.0°F)

3 > 40.0°C (> 104.0°F) for ≤ 24 hrs

4 > 40.0°C (> 104.0°F) for > 24 hrs

Elevated Pulse Rate

For this study, a **pulse** rate of \geq 150 beats per minute maintained for a minimum of 10 minutes will be considered severe and generate an alert.

Elevated Respiratory Rate

For this study, an elevated respiratory rate of \geq 25 breaths per minute maintained for a minimum of 10 minutes is considered severe and will generate an alert.

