2.1 Objectives and Endpoints

Objectives	Endpoints	
Primary		
• To determine the safety of outpatient blinatumomab administration, during the MDMP (defined as the first 3 days of cycle 1 and first 2 days of cycle 2 of outpatient blinatumomab infusion)	 Grade 3 and/or 4 CRS, NT or any adverse event (AE) requiring hospitalization (SAE) during MDMP. 	
Secondary		
• To determine the time from first detection of grade 3 or 4 vital sign, or significant clinical change to therapeutic intervention (any measurable action taken by or performed on the subject due to onset of the clinical parameters described above) during the MDMP	• Time (in minutes) from first onset of fever, hypotension, hypoxia, other grade 3 or 4 vital sign including seizure or neurological change (grade 3-limiting self-care activities of daily living [ADL]) to therapeutic intervention.	
 Evaluate the safety and tolerability of blinatumomab administered exclusively as an outpatient 	 Treatment-emergent adverse events (TEAE) and adverse events of interest in particular CRS and NT. 	
• Evaluate the impact of complete outpatient blinatumomab treatment on patient-reported outcome (PRO), global health status (GHS), and quality of life (QoL).	 European Organisation for Research and Treatment of Cancer (EORTC) validated electronic version of QLQ-C30. 	
Estimate healthcare resource utilization associated with treatment-related AEs	 Treatment-related TEAEs that resulted in hospitalizations. Treatment-related TEAEs that resulted in surgeries. Treatment-related TEAEs that resulted in the use of concomitant medications. Treatment-related TEAEs that resulted in the use of device/procedure intervention. 	

ADL = activities of daily living; AE = adverse event; CG = caregiver; CRS = cytokine release syndrome; EMS = Emergency Medical Service; EORTC = European Organisation for Research and Treatment of Cancer; GHS = global health status; HCP = Health Care Provider; IV = intravenous; MDMP = mandatory device monitoring period; NT = neurotoxicity; PO = by mouth; PRO = patient-reported outcomes; QLQ-30 = Quality of Life of Cancer Patients; QoL = quality of life; SAE = serious adverse event; TEAE = treatment-emergent adverse event.

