For the purpose of this study, the mandatory device monitoring period (MDMP) is defined as the first three days of cycle 1 (72 hours) and the first 2 days of cycle 2 (48 hours) of blinatumomab infusion.

Therapeutic Intervention (TI)

Therapeutic intervention is any measurable action taken by the subject or performed on the subject as a result of the onset of the clinical parameters described. Such actions may include:

- Advised subject to go to hospital/ER immediately
- Advised subject to call 911 immediately
- Advised to suspend blinatumomab
- Advised to take antipyretic (e.g. acetaminophen)
- Advised subject to take dexamethasone
- Advised to suspend blinatumomab and take antipyretic
- Advised to suspend blinatumomab and take dexamethasone
- Advised to take other medication

• Other (if Other, describe the intervention)

Time to Therapeutic Intervention (TTI)

Time to therapeutic intervention is the time between the delivery of the device alert or unscheduled contact with HCP by subject/CG to report a change to the time of initiation of the therapeutic intervention.

TTI will be calculated as duration (in minutes) from time of the device alert (alarm triggered) to the time of initiation of the therapeutic intervention (i.e. when HCP silenced the alarm and advised an intervention).

If there is a case where the alarm is triggered, and the HCP advised an intervention, but event is not resolved and subject/CG presses the alarm again then that would be considered as a separate event (as alarm ID will be different) to calculate TTI.

TTI will be calculated for all the valid alarm triggers which leads to an intervention. If the calculated TTI is considered incongruous (i.e. more than 15min.) then a query will be entered in DIIR log.

All the scenarios defined below will be considered as invalid for calculation of TTI:

- If no intervention is required (e.g. technical issues) corresponding to an alarm.
- If intervention time is prior to the time of device alert (alarm triggered).

Treatment-emergent Adverse Event

Treatment-emergent Adverse Event is defined as adverse events starting on or after first dose of blinatumomab as determined by "Did event start before first dose of investigational product" equal to "No" or missing on the Events eCRF and up to the end of study visit.

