9.5.2 Analyses of Secondary Efficacy Endpoint(s)

Not Applicable.

9.5.3 Analyses of Exploratory Efficacy Endpoint(s) Not Applicable.

- 9.6 Safety Analyses
- 9.6.1 Analyses of Primary and Key Secondary Safety Endpoint(s)

Endpoint	Statistical Analysis Methods				
Primary	Subject incidence rate of primary endpoint (grade 3 or 4 CRS, NT or				
	any adverse event resulting in hospitalization during MDMP) will be				
	summarized and accompanied by 2-sided 95% exact binomial				
	confidence intervals (Clopper and Pearson, 1934). This endpoint will				
	be analyzed using PAS and repeated using interim analysis set.				
Кеу	TTI as defined in section 5 of SAP will be summarized as continuous variable with number of non-missing and valid TTI with mean, median, standard deviation, minimum and maximum.				
Secondary					
	Number and percent of subjects who had received at least one				
	therapeutic intervention (as defined in section 5 of SAP) will be				
	summarized in total and by types of intervention. Total number of				
	therapeutic interventions and type of therapeutic intervention will be				
	tabulated.				
	Number and percent of subjects with at least one alarm triggered will				
	be summarized in total and by reasons of alarm trigger. Total number				
	of alarms triggered and reasons for each alarm trigger (as specified				
	below) will be tabulated.				
	Technical				
	Patient message				
	Physiological – Axillary temperature				
	Physiological – Systolic blood pressure				
	Physiological – Spo2				
	Physiological – Respiratory rate				
	Physiological – Pulse rate				
	Descriptive statistics for number of alarms triggered and therapeutic				
	interventions received per person will also be presented.				
	This endpoint will be analyzed using PAS and repeated using interim analysis set.				

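### The key secondary objective, its endpoint, Protocol 9.4.2.3.1 and the SAP do not time the same events, and the SAP's single pooled TTI summary cannot be separated by severity or alarm reason

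*SAP*

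**What the plan says.** The event set for time to therapeutic intervention (TTI) is described in five places.

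- **Objective** (Protocol section 3, SAP 2.1): "To determine the time from first detection of grade 3 or 4 vital sign, or significant clinical change to therapeutic intervention".
- **Endpoint** (same tables): "Time (in minutes) from first onset of fever, hypotension, hypoxia, other grade 3 or 4 vital sign including seizure or neurological change", the neurological change being one of grade 3. Fever, hypotension and hypoxia carry no grade; the grade qualifies the other vital signs.
- **Protocol 9.4.2.3.1**: time from first onset of the endpoint event, summarized for those who experience it.
- **Sample size** (Protocol 9.2, SAP 3.2): about 17 subjects are expected to have "the primary endpoint which should provide an initial indication of the timeliness of the therapeutic intervention".
- **SAP section 5**: "TTI will be calculated for all the valid alarm triggers which leads to an intervention". An alarm is invalid "If no intervention is required (e.g. technical issues) corresponding to an alarm", or if the intervention time precedes the alert. When a subject or caregiver presses the alarm again after an unresolved event, "then that would be considered as a separate event (as alarm ID will be different) to calculate TTI".

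SAP 9.6.1 gives one TTI summary. Alarm counts are broken down by reason and interventions by type, but TTI is broken down by neither. SAP section 10 lists the changes from the protocol and does not include this one.

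**The concern.** The trial asks how quickly a patient who deteriorates at home is treated. The alarm thresholds are set low on purpose, and the listed interventions include advice to take an antipyretic. A temperature alarm at 38.0°C answered with acetaminophen is therefore a valid TTI, as is a patient message about a mild symptom that led to any advice. These enter the same mean and median as the response to a seizure or a sharp fall in blood pressure. Because the alarm is the unit, a subject with many minor alarms also weighs more than a subject with one serious event.

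At stake is interpretation. A reader of the report would take the pooled median as the answer to the stated objective, and no planned table would show whether it is.

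**Working it through.** **1. The plan's own figures.** With N = 45 and p = 0.38 (Protocol 9.2), 45 × 0.38 = 17.1, which gives the stated 17. The two-sided 95% Clopper-Pearson upper limit, averaged over Binomial(45, 0.38), is 53.52%, which gives the stated 53.5%. The 2.5% and 97.5% points of that binomial are 11 and 24 subjects. The sample-size arithmetic is sound; the issue is which events are timed.

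**2. Alarm triggers against the endpoint.** Triggers are from Protocol Table 1-1 and SAP 9.6.1, definitions from Protocol Appendix 8.

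| Trigger (if it led to an intervention) | Covered by the endpoint as written? |
|---|---|
| Temperature ≥ 38.0°C | Yes, as fever, although this is grade 1; grade 3 is "3 > 40.0°C (> 104.0°F) for ≤ 24 hrs" |
| Systolic BP ≤ 100 mmHg or a 20% fall | Yes, Appendix 8 hypotension |
| Oxygen saturation ≤ 92% | Yes, Appendix 8 hypoxia |
| Pulse ≥ 150, respiratory rate ≥ 25 | Yes, if the Appendix 8 label severe is read as grade 3 or 4 |
| Pulse ≤ 60, respiratory rate ≤ 10 | No: not named and not graded |
| Patient message | Only for seizure or grade 3 neurological change, or if it reports another listed sign |

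The SAP times every row. Its set is therefore wider than the endpoint, and the endpoint is wider than the grade 3 or 4 vital signs of the objective.

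**3. How large the milder share could be.** The documents give no alarm rates, so this is an assumption with a range. Let 20% to 80% of the 45 subjects have 1 to 5 milder alarms that lead to an intervention, and let 17 primary-endpoint subjects give one TTI each.

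- Low end: 0.20 × 45 × 1 = 9; 9 / (9 + 17) = 35%.
- High end: 0.80 × 45 × 5 = 180; 180 / (180 + 17) = 91%.

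Some of these milder alarms would be fevers that the endpoint covers, so this is not the share outside the endpoint.

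**4. What pooling could do.** Assume lognormal TTIs with log-scale SD σ = 0.6, severe share w, and medians S (severe) and M (mild). The pooled median m solves

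w Φ((ln m − ln S)/σ) + (1 − w) Φ((ln m − ln M)/σ) = 0.5.

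| S, M (min) | w | Pooled median (min) | Against S |
|---|---|---|---|
| 12, 6 | 10% | 6.4 | −47% |
| 12, 6 | 40% | 7.9 | −35% |
| 6, 12 | 10% | 11.3 | +88% |
| 6, 12 | 40% | 9.2 | +53% |

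If S = M, the pooled median equals both and the mix has no effect. Every input in this step is assumed; it shows the mechanism, not an estimate for this trial.

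**The case against.** The strongest reply is that the SAP rule mostly follows the endpoint as written. Fever, hypotension and hypoxia carry no grade there, and Appendix 8 defines them for this study at the alarm thresholds. The objective also includes significant clinical change. The protocol's TTI footnote starts the clock at any device alert or unscheduled contact and counts oral medication as an intervention. Cytokine release syndrome must include fever at onset, so early fever alarms are part of what the monitoring is for. This stands: timing a grade 1 fever fits the endpoint, and a main table limited to grade 3 or 4 fever would replace the endpoint rather than restore it.

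Alarms that need no intervention are excluded, so a slow pulse that nobody acted on does not enter. This also stands. The amendment's remark that most initial alarms were technical does not show that mild clinical alarms predominate.

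On the 17 subjects, the sample size rests on feasibility and offers only an initial indication of timeliness. No separate table is promised, and their valid alarms are already in the pooled summary. A subset defined partly by hospitalization is also partly selected on the response being timed, since advice to go to hospital is a listed intervention. These are reasons to make such a table supportive.

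What the reply does not cover is low pulse, low respiratory rate and messages about mild symptoms; the loss of first onset; the absence of any split of TTI; and the silence of SAP section 10. The SAP's decision not to run subgroup analyses does not answer this, because a split by type of event is not a subgroup of subjects.

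**Conclusion.** The point holds as a mismatch of event sets that the SAP neither resolves nor declares. Milder alarms may dominate the pooled TTI, and no planned table separates them.

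A reader might infer that mild fever and slow-pulse alarms will determine the result, or that timing a grade 1 fever breaches the protocol. The documents support neither: they give no alarm counts or response times by grade, and the endpoint lists fever without a grade. Nor is it right that the primary-endpoint subjects go unanalysed; they are included but cannot be seen separately.

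The size of any distortion is unknown in both magnitude and direction. The 35% to 88% in the illustration rests wholly on the assumed medians, spread and severe share, and falls to zero if response time does not depend on severity. The remedy is cheap and should be made before database lock.

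**What to change.** In SAP section 5 and 9.6.1:

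1. Base the key secondary TTI table on the first onset of an event that meets the endpoint as written, as Protocol 9.4.2.3.1 states. Use the Appendix 8 definitions: fever, hypotension, hypoxia, pulse ≥ 150, respiratory rate ≥ 25, seizure, and grade 3 neurological change. Say whether first means per subject or per type of sign.
2. Show TTI by alarm reason, with fever split by the grade of the recorded temperature.
3. Keep the all-alarm TTI as supportive. Add a supportive TTI summary for subjects with a primary endpoint event (about 17 expected, 95% range 11 to 24), with a note that hospitalization partly defines this subset and is itself a possible response.
4. List the change in SAP section 10.

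The axillary fever threshold also needs reconciling, because it decides which readings count as fever. It is given as 37.0°C (99.4°F), but 37.0 × 1.8 + 32 = 98.6°F, and (99.4 − 32) / 1.8 = 37.4°C.

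The cost is SAP text and a few tables from device and Events data already collected. The main table will hold fewer observations. Neither document describes a link between alarm IDs and graded adverse events, so neurological events may have to be matched by subject and time. Fever can be split on the temperature reading, but the grade of cytokine release syndrome cannot be read from an alarm, because it depends on support given later.

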6.1 Full Analysis Set (FAS)

Full Analysis Set (FAS) will include all subjects enrolled into the study.

6.2 Safety Analysis Set (SAS)

Safety analysis set will include all enrolled subjects who receive at least 1 dose of blinatumomab. The analysis of secondary safety and resource utilization endpoints will be conducted on the SAS.

6.3 Primary Analysis Set (PAS)

Primary analysis set will include all subjects in the SAS who were not replaced (see **Section 8.3** for the criteria of subject replacement). The analysis of primary and the **key** secondary endpoint will be conducted on the PAS.

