- Oral dose(s) of steroid available at home, to be taken under HCP direction.
- On day 1 of cycle 1, subject to remain at infusion center for 5 hours after initiating blinatumomab.
 On day 1 of cycle 2, subject to remain at infusion center for 2 hours after initiating blinatumomab.
 - For cycles 3 and 4, HCP is to follow product information regarding patient monitoring
- Either
 - Abnormal VS (persistent for ≥ 10 minutes).
 - or change in clinical status by patient or CG report
- Will generate an immediate alert to HCP
- HCP will contact/communicate with Subject /CG via phone/tablet video monitoring
- HCP response per monitoring algorithm (panel 2)
- HCP will be able to contact Subject/CG for any concerns in absence of an alert
- Subject /CG will be able to contact HCP, or Emergency services directly as needed

BP = blood pressure; HCP = healthcare professional; IP = Investigational product

Date: 21 April 2022 Page 20 of 108

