8.2.2.1 Digital Health Device Monitoring of Vital Signs During the Mandatory Monitoring Period

During the MDMP, subjects will wear the CWHMS (**CH** wearable device and axillary temperature patch) continuously 24 hours a day. **Subjects must constantly remain within range of the (current health provided) home hub WiFi device for the first 24 hours of the study.** After the first 24 hours, subjects may be allowed to remove 1 or all of the devices for a maximum of 1 hour per day **only after first notifying HCP.** This will allow subjects to attend to personal activities such as taking a bath or shower. Subject must be clinically stable with normal vitals and no evidence of NT prior to the start of the 60-minute period. This break must be coordinated with the HCP, as no data will be transmitted during this period. It is recommended that subjects use this time **to charge the CH wearable device.** It is also strongly encouraged that the subjects **charge** the CH wearable device at approximately the same time each day.

Vital signs (**pulse rate**, **respiratory rate**, oxygen saturation, and axillary temperature) will be measured continuously using CWHMS, as specified in the Schedule of Activities (Table 1-2). There will be no data transmission to HCP while subjects are transported to home from the outpatient facility. Vital sign data will be stored but not transmitted in real time.

Non-invasive BP will also be performed as specified in the Schedule of Activities (Table 1-2). Vital signs will be available as a constant live feed to the HCP for the entire MDMP. **Health and technical alarms**/alerts will indicate when a vital sign is outside of the preset parameters. Details of the data that will be monitored using the digital health devices are described in detail in Section 6.1.2.

Sites will be given the option to utilize a nursing triaging service provisioned by CH to act as their designee to acknowledge and respond to health and technical

Date: 21 April 2022 Page 58 of 108

alarms during a subject's MDMP. This service can be requested by the site on a subject-by-subject basis.

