9.3 Analysis Sets, Subgroups, and Covariates

9.3.1 Analysis Sets

Safety Analysis Set (SAS)

All enrolled subjects who receive at least 1 dose of blinatumomab. The analysis of secondary safety and resource utilization endpoints will be conducted on the SAS.

Primary Analysis Set (PAS)

All subjects in the SAS who were not replaced (see Section 4.2.1). The analysis of primary and key secondary endpoint will be conduct on the PAS.

Patient Reported Outcomes Analysis Set

The Patient Reported Outcomes (PRO) Analysis Set will include all subjects in the SAS with a non-missing baseline and at least 1 non-missing post-baseline result for EORTC QLQ-C30. Subjects will be included in the analysis of each EORTC QLQ-C30 for which they have non-missing data.

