4.2 Subgroups

Due to small sample size, subgroup analysis will not be performed.

5. Definitions

Age at Enrollment:

Subject age at enrollment will be collected in years in the clinical database.

Adverse Event During the MDMP

Adverse event during the MDMP is defined as an adverse event that started within 72 hours after the first dose of blinatumomab in cycle 1 and within 48 hours after the first dose of blinatumomab in cycle 2.

For adverse events with missing start time, the adverse event during the MDMP is defined as an adverse event that started within 3 days after the first dose date of blinatumomab in cycle 1 and within 2 days after the first dose date of blinatumomab in cycle 2.

Baseline

The baseline value will be defined as the value measured on day 1 of the first cycle before start of the first infusion of blinatumomab. If a cycle 1 day 1 value is not available, the latest value before the day 1 of the start of blinatumomab infusion may be used.

Cumulative Dose of Blinatumomab

The cumulative dose in μg is defined as the following with summation over infusions:

 \sum Duration of infusion [days] for each dose received × dose received [μ g/day].

Cumulative dose will be calculated within a cycle and across all cycles.

Duration of Therapy

For each infusion episode within a cycle, the duration of exposure will be calculated by subtracting the start date and time from the stop date and time. If either a start or stop time is missing, only the date portion will be used in calculating the duration of a specific

infusion. For each cycle, the duration will be the sum of the individual infusion durations within that cycle. For the entire study, the duration will be the sum of the durations across cycles. The duration will be rounded to the nearest day.

End of Study

The end of study date is defined as the date when the last subject across all sites is assessed or receives an intervention for evaluation in the study (i.e. last subject last visit).

End of Study Visit

The end of study visit will occur 30 days (\Box 3 days) after the last dose of blinatumomab is given. The end of study visit will occur after cycle 3 or 4 for subjects who chose these optional cycles. End of study visit date for each subject will be recorded on the End of Study CRF page.

Enrollment Date

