8.3 Handling of Missing and Incomplete Data

In general, missing data will be treated as missing, unless stated otherwise. Missing response for questions in EORTC QLQ-C30 PRO will be imputed as defined in section 5 of this SAP.

The handling of incomplete and partial dates for adverse events and concomitant medications are described in Appendix D.

Subjects will be replaced for analysis if the outpatient monitoring during blinatumomab infusion is not established.

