9.6.2 Adverse Events

The Medical Dictionary for Regulatory Activities (MedDRA) version 25.0 or later will be used to code all events to a system organ class (SOC) and a preferred term (PT). Severity will be coded by using CTCAE version 5.0 or later.

Subject incidence of all, serious, grade 3 and above, leading to withdrawal of investigational product, leading to interruption of investigational product, fatal, treatment-related, treatment-related serious, and treatment-related grade 3 and above TEAEs will be tabulated by SOC and PT in descending order of frequency. In addition, treatment-emergent adverse events will be summarized by SOC, PT, and grade; and by PT only in descending order of frequency.

Treatment-emergent events of interest (EOIs) will be summarized by EOI category and preferred term. In addition, for each EOI category, the subject incidence of all, serious, grade 3 and above, grade 4 and above, fatal, leading to withdrawal of IP, leading to interruption of IP will be summarized. Time to onset, duration, number of resolved events for select EOIs (infection, neurologic events and CRS) will also be summarized.

To support estimation of healthcare resource utilization associated with treatment-related AEs, the summary of subject incidence treatment related TEAEs will be provided for treatment related TEAEs that resulted in hospitalizations, treatment related TEAEs that resulted in surgeries, treatment related TEAEs that resulted in the use of concomitant medications, treatment related TEAEs that resulted in the use of device/procedure intervention (see SAP section 10 'Changes from Protocol-specified Analyses' for details on updates to endpoints of secondary objective for estimation of healthcare resource utilization).

The above analyses will be performed using subjects in the SAS.

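### The primary MDMP safety composite excludes dosed subjects under an undefined replacement rule, and no all-dosed run is planned beside it

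*SAP*

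**What the plan says.** **Population.** The SAS is everyone enrolled who received at least one dose (Protocol 9.3.1, SAP 6.2). For the PAS, SAP 6.3 states: "Primary analysis set will include all subjects in the SAS who were not replaced". Protocol 9.3.1 defines it the same way and points to its Section 4.2.1. Both documents assign the primary endpoint to the PAS. The SAP 9.6.1 table says the endpoint will "be analyzed using PAS and repeated using interim analysis set". SAP Section 6 lists no interim analysis set.

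**Replacement rule.** SAP 8.3: "Subjects will be replaced for analysis if the outpatient monitoring during blinatumomab infusion is not established". Protocol 4.2.1 and 9.3.4 have the same sentence, a further line on removal from investigational product for disease progression, and a statement that confines replacement status to internal data analysis. SAP Section 10 records the removal of the last two items. The exclusion from the primary set remains.

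**Event window.** SAP Section 5 counts "an adverse event that started within 72 hours after the first dose of blinatumomab in cycle 1", and uses a 48-hour window for cycle 2.

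**Other outputs.** SAP 9.6.2 plans whole-study adverse event tables and says "The above analyses will be performed using subjects in the SAS". SAP 9.7.3 plans exact intervals for treatment-emergent events (TEAEs) that led to hospitalization, surgery, medication or device use. SAP 6.2 places resource-use endpoints on the SAS.

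**The concern.** The primary result is a safety rate. Its denominator leaves out some people who started outpatient infusion, under a rule that different people could apply differently. Neither document says how much device data, over what time or in which cycle, counts as established monitoring, who decides, or whether the decision must come before outcomes are known. The study is open-label and MDMP events count from the first dose, so on the text the decision could follow an early event.

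The reported rate and interval would then describe only subjects in whom monitoring was judged to have been set up, which may not be the rate in everyone who began outpatient treatment. The bias could go down if subjects with early events were replaced, or up if event-free technical failures were. No hypothesis test or formal stopping rule uses the rate (Protocol 9.1 and 9.4.1.1). But in an estimation-only study the rate and its interval are the result, so readers need to know whom they describe.

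**Working it through.** **Step 1. Inputs.** From SAP 3.2: about 45 subjects, an assumed event probability of 38%, about 17 subjects with the endpoint, and an expected upper limit of 53.5%. From SAP 9.6.1: two-sided 95% exact (Clopper-Pearson) intervals. The number of dosed subjects who will be replaced is not given, so k = 1 and k = 5 are assumptions for illustration.

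**Step 2. The plan's own figure.** With x events in n subjects, the lower limit is the 2.5% quantile of Beta(x, n − x + 1) and the upper limit is the 97.5% quantile of Beta(x + 1, n − x). Expected events are 45 × 0.38 = 17.1. For 17/45 = 37.8% the interval is 23.8% to 53.5%. Averaging the upper limit over Binomial(45, 0.38) also gives 53.5%. The sample-size statement is correct.

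**Step 3. Which outputs include a replaced dosed subject?**

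| Output | Population | Period | Primary composite? |
|---|---|---|---|
| SAP 9.6.1, primary | PAS: excluded | MDMP | Yes |
| SAP 9.6.1, repeat | Interim analysis set: undefined | MDMP | Yes |
| Protocol 9.4.2.3.2, MDMP adverse event repeat | PAS: excluded | MDMP | No |
| SAP 9.6.2, adverse event tables | SAS: included | Whole study | No |
| SAP 9.7.3, hospitalization rate | SAS (SAP 6.2): included | Whole study | No |

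The interim repeat cannot be taken as an all-dosed run, because the review schedule in SAP 7.1 counts only non-replaceable subjects. For the last row, SAP 2.1, 9.6.2 and Section 10 restrict the endpoint to treatment-related TEAEs, whereas 9.7.3 does not, so its content is unsettled. No row gives the MDMP composite on all dosed subjects. SAP 9.2 reports how many were dosed, so the number replaced follows as SAS minus PAS. Reasons for replacement and those subjects' MDMP events are not planned.

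**Step 4. Illustration A: 45 dosed, 17 events, k excluded, of whom e had an event.** PAS rate = (17 − e)/(45 − k).

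| k | e | PAS rate (95% CI) | Shift from 37.8% |
|---|---|---|---|
| 1 | 1 | 16/44 = 36.4% (22.4 to 52.2) | −1.4 points |
| 1 | 0 | 17/44 = 38.6% (24.4 to 54.5) | +0.8 points |
| 5 | 5 | 12/40 = 30.0% (16.6 to 46.5) | −7.8 points |
| 5 | 0 | 17/40 = 42.5% (27.0 to 59.1) | +4.7 points |

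**Step 5. Illustration B: PAS refilled to 45 with 17 events (37.8%).** All-dosed rate = (17 + e)/(45 + k). With k = 1 it is 17/46 = 37.0% (23.2 to 52.5) or 18/46 = 39.1% (25.1 to 54.6). With k = 5 it runs from 17/50 = 34.0% (21.2 to 48.8) to 22/50 = 44.0% (30.0 to 58.7).

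**Step 6. How extreme are the five-subject cases?** If five were drawn from the 45 regardless of outcome, the chance that all five had events is C(17,5)/C(45,5) = 6,188/1,221,759 = 0.5%. The chance that none did is C(28,5)/C(45,5) = 98,280/1,221,759 = 8.0%.

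**Step 7. Scale.** The half-width at 17/45 is (53.5 − 23.8)/2 = 14.9 points. The largest shift above is 7.8 points.

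**The case against.** *The population is coherent.* The study tests outpatient dosing with remote monitoring, so a primary set of subjects in whom monitoring was set up is defensible. This stands. It is why the SAS run belongs beside the PAS and does not replace it.

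*Early events need not lead to replacement.* A reader might infer a mechanism from Protocol Table 1-1 ("On day 1 of cycle 1, subject to remain at infusion center for 5 hours after initiating blinatumomab") and Protocol 8.2.2.1 ("There will be no data transmission to HCP while subjects are transported to home from the outpatient facility"): a subject who has an event at the center or in transit is admitted, never has monitoring at home, and is dropped. The documents do not support this as more than an unresolved possibility. The rule speaks of outpatient monitoring, not home monitoring. Protocol Table 1-2 and 8.2.2.1 have the devices worn round the clock during the MDMP, and vital signs recorded in transit are stored. No passage makes an event a ground for replacement. What remains is that no passage rules it out. Nor do the documents say how to class a subject removed after a second failure to comply with the devices (Protocol 6.4).

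*Replaced subjects' events do not vanish.* This also stands. The SAS tables in SAP 9.6.2 include them, with time to onset for cytokine release syndrome and neurologic events. But they are pooled over the whole study, without the MDMP composite or its interval.

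*Few may be replaced, and no decision hangs on the rate.* Protocol Table 1-2 provides a device trial of at least 24 hours at screening and duplicate devices in each kit. No document shows that replacement was frequent or related to outcome. This limits the weight of the point but does not remove the gap.

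**Conclusion.** The point holds as a gap in the planned analysis. The primary composite is planned only on a set that drops dosed subjects under a rule with no operational definition, and on an undefined interim set. The all-dosed version is not planned. The SAP also removes the protocol's limit of replacement status to internal analysis while keeping the exclusion in the primary set.

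A reader might go further and infer that the primary rate will be biased downward, or that the PAS is the wrong primary set. The documents support neither. The number replaced, its relation to outcome and the direction of any bias are all unknown. Under the assumed counts, one exclusion moves the rate by about 1 point. Five exclusions move it by at most 7.8 points, in a case that would be rare if exclusion were unrelated to outcome. Both are within the half-width of about 15 points. What is at stake is whether the reported rate can be read as applying to everyone who started outpatient treatment.

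**What to change.** **SAP 9.6.1:** also run the primary composite with its exact interval on the SAS, and show it beside the PAS result. The PAS stays primary. List each replaced dosed subject with the reason and any MDMP events.

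**SAP 8.3:** set the criterion and time point for established monitoring and say who decides. State that an adverse event after the first dose cannot in itself make a subject replaceable.

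**SAP Section 6:** define the interim analysis set or delete the reference to it.

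**Cost:** some SAP wording and one or two extra tables from data already collected. Sample size, study conduct and the primary set do not change. The downside is that the SAS rate may be less favourable than the PAS rate.
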